
Table 1: Time and Events Schedule
 
9.2 Efficacy Evaluations
 
9.2.3 CRAB Criteria-related Laboratory Assessments
 
9.2.4 Myeloma Protein Measurements in Serum and Urine
 
9.2.5 β2-microglobulin and Lactate Dehydrogenase
 
9.2.6 Bone Marrow Examination
 
Assessment of Bone Disease
 
9.7 Safety Evaluations
 
9.5 Patient-reported outcomes
 
9.6 Medical Resource Utilization
	
Central laboratory testing will be discontinued.
 
Pre-PD follow up and PD assessments:
 
 • Disease evaluations should continue according to Time & Events Schedule, by local assessment • Only disease progression by investigator via local assessment will be reported to the Sponsor. • Assessment of response for disease evaluations and local laboratory and imaging results will not be reported to the Sponsor. 
Post-PD follow-up:
 
PRO and MRU collection at Months 12 and 18 in the have been discontinued.
	
Post primary analysis, central laboratory testing and central imaging are no longer required.
 
Post primary analysis, PRO and MRU collection at Months 3 and 6 are considered sufficient.

Table 1: Time and Events Schedule
 
9.4 Biomarkers
 
Table 10
	
Central Laboratory Biomarker assessments will be discontinued.
	
Post primary analysis, biomarker analyses are no longer required.

9.3 Pharmacokinetics and Immunogenicity
	
Immunogenicity and PK assessments will no longer be collected.
	

SYNOPSIS
 
Table 1: Time and Events Schedule
 
Table 2: Daratumumab Administration (Arm B Only)
 
9.1.1 Overview
 
9.2 Efficacy Evaluations
 
9.3.2 Analytical Procedures
 
9.4 Biomarkers
 
9.5 Patient-reported Outcomes
 
9.6 Medical Resource Utilization
	
Home health care visits have been removed throughout the protocol.
	
Home health care visits are no longer available.
 
NOTE: Tele health visits (conducted via phone or video conference) may continue as deemed necessary.

11.12 Data Monitoring Committee
	
The IDMC will be discontinued once the primary analysis endpoint has been achieved.
	
IDMC will no longer be required.

Throughout the protocol
	
Minor grammatical, formatting, or spelling changes were made.
	
Minor errors were noted.

SYNOPSIS

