	Notes	Active Monitoring (Arm A; 12-week disease evaluations) / Treatment Phase (Arm B; 4-week treatment cycles after Cycle 6) ^a (up to 39 cycles or 36 months, whichever occurs first)						End of Active Monitoring/ End of Treatment	Pre-PD Follow-up	PD	Post-PD Follow-up	
		Screening (within 35 days before randomization)	C1-2		C3-6		C7-39					
		D1 ^b	D8	D15	D22	D1	D15	D1	30 (±3) days after the last Daratumumab dose ^c	every 12 weeks (±7 days)	at least every 6 months (until end of study)	
		Daratumumab (Arm B): Continuous from the time of signing of ICF until 30 days after last daratumumab dose, or until start of next therapy, whichever is earlier.										
Survival, Second primary malignancies		Throughout study until the end of study, and at a frequency of at least every 12 weeks until PD.										X
Best response to first-line MM treatment, PFS2	Investigator review; no central laboratory testing											X
Biomarkers Assessments. Per Amendment 6 all biomarker assessments by central lab are discontinued. FISH testing at PD to be performed locally.												
Whole blood (biomarkers)	Cytometry by time of flight	X	Week 24, Week 48, Week 96, and at suspected CR (±1 month with disease evaluations)					X		X		
	PBMCs	X										
	Plasma	X	Every 12 months from C1D1 (±1 month with disease evaluations)							X		
Stool (biomarkers)	Microbiome	X	Week 24 and at suspected CR (±1 month with disease evaluations)							X		
Bone Marrow aspirate ^m	Cytogenetics by FISH ^k	X								X		

Notes	Active Monitoring (Arm A; 12-week disease evaluations) / Treatment Phase (Arm B; 4-week treatment cycles after Cycle 6) ^a (up to 39 cycles or 36 months, whichever occurs first)						End of Active Monitoring/ End of Treatment	Pre-PD Follow-up	PD	Post-PD Follow-up
	Screening (within 35 days before randomization)	C1-2		C3-6		C7-39				
		D1 ^b	D8	D15	D22	D1	D15	D1		

- a. Treatment Phase (Arm B): daratumumab SC administered weekly in Cycles 1 and 2, every 2 weeks for Cycles 3 to 6, and every 4 weeks thereafter until 39 cycles or 36 months (whichever occurs first) or confirmed PD.
- b. C1D1 should occur within 5 days after randomization (Arm B).

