2.1.2. Endpoints

Primary Endpoint

The primary endpoint of this study is PFS (defined as the time from the date of randomization to the date of initial documented progression to MM according to the IMWG diagnostic criteria for MM or the date of death, whichever occurs first).

Secondary Endpoints

To demonstrate additional clinical benefit, the following secondary endpoints will be evaluated:

- Time to biochemical or diagnostic (SLiM-CRAB) progression defined as the earlier of time to the earlier of biochemical progression or diagnostic (SLiM-CRAB) progression (see Section 9.2.2)
- Overall response rate (ORR), defined as, the proportion of subjects with a PR or better as defined by the IMWG response criteria
- Complete response (CR) rate, defined as, the proportion of subjects with a CR (or better) as defined by the IMWG response criteria
- Time to first-line treatment for MM, defined as, the time from the date of randomization to the date of the first-line treatment for MM
- Progression-free survival on first-line treatment for MM (PFS2), defined as, the time from the date of randomization to the date of documented progressive disease (PD) on the first-line treatment for MM or death, whichever comes first
- Overall survival (OS), defined as, the time from the date of randomization to the date of death
- Incidence of MM with adverse prognostic features, which include International Staging System Stage III (based on β 2-microglobulin and albumin) and adverse cytogenetic characteristics

- Serum daratumumab PK concentrations and parameters including minimum observed concentration (C_{min}) and maximum observed concentration (C_{max})
- Incidence of anti-daratumumab antibodies and anti-rHuPH20 antibodies
- Change from baseline in global health status and emotional functioning scales of the European Organization for Research and Treatment of Cancer (EORTC) quality of life questionnaire (QLQ)-C30, future perspective scale of the EORTC QLQ-MY20, and utility and visual analog scale of the European Quality of Life Five Dimensions Questionnaire (EQ-5D-5L)
- Duration of response, defined as date of onset of first response until date of disease progression or death
- Time to response, defined as the time from randomization until onset of first response

Exploratory Endpoints

- Identification of novel biomarkers in relation to PFS/OS

Refer to Section 9, Study Evaluations for evaluations related to endpoints.

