Daratumumab is an immunoglobulin that may interfere with clinical SPEP/SIFE assessments. In cases in which daratumumab interference is suspected, a reflex assay confirming the presence of daratumumab will be performed ([Attachment 7](#)). In cases where CR or sCR is suspected and the reflex assay confirms that daratumumab is present on SPEP/SIFE, additional clinical assessments will be triggered to confirm the CR/sCR. A subject who meets all other clinical criteria for CR/sCR, and who has daratumumab interference confirmed by the reflex assay, will be considered a CR/sCR.

9.2.5. β 2-microglobulin and Lactate Dehydrogenase

As per protocol Amendment 6, β 2-microglobulin and lactate dehydrogenase at time of disease progression will no longer be analyzed by the central laboratory and will only be analyzed locally.

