## **5.3.7. Incidence of MM with adverse prognostic factors**

### **5.3.7.1. Definition**

Incidence of MM with adverse prognostic factors is defined as progression to International Staging System (ISS) III MM (based on  $\beta$ 2-microglobulin), MM with adverse cytogenetic characteristics (FISH findings of del(17p), t(4;14), t(14;16) or amp(1q21)), or r-ISS III MM (based on  $\beta$ 2-microglobulin, LDH and adverse cytogenetic characteristics).

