### **5.3.7.2. Analysis Methods**

Proportions of subjects who progress to MM with adverse prognostic factors will be tabulated and two-sided 95% Clopper-Pearson exact confidence intervals (CI) will be presented by treatment group.

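### After Amendment 6 the laboratory and FISH results that define MM with adverse prognostic features are still obtained at progression, but the plan does not have them reported to the sponsor

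*Protocol*

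**What the plan says.** **What is reported.** For pre-progression follow-up and progression assessments, the Amendment 6 summary of changes states: "Only disease progression by investigator via local assessment will be reported to the Sponsor". The next bullet adds: "Assessment of response for disease evaluations and local laboratory and imaging results will not be reported to the Sponsor".

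**What is still done.** Protocol 9.2.5 treats both serum markers, β2-microglobulin and LDH, alike: "lactate dehydrogenase at time of disease progression will no longer be analyzed by the central laboratory and will only be analyzed locally". The biomarker block of Table 1 in the Time and Events Schedule has "FISH testing at PD to be performed locally", and 9.2.6 and Table 10 agree. Table 1 also keeps albumin at progression.

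**What depends on it.** Protocol 2.1.2 retains the secondary endpoint "Incidence of MM with adverse prognostic features, which include International Staging System Stage III". Staging there uses β2-microglobulin and albumin; adverse cytogenetics is the other component. SAP 5.3.7.1 reads "Incidence of MM with adverse prognostic factors is defined as progression to International Staging System (ISS) III MM" and adds adverse FISH findings and r-ISS III, which brings in LDH. SAP 5.3.7.2 says "Proportions of subjects who progress to MM with adverse prognostic factors will be tabulated", with exact 95% intervals by arm. It gives no denominator, no cutoff and no category for missing results.

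**Timing.** The summary of changes says the primary analysis had concluded by Amendment 6 (9 September 2024). Protocol 3.1 puts the end of study about 8 years after first randomization and reports the later data in an addendum to the Clinical Study Report. The latest SAP amendment is dated 16 December 2020.

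**The concern.** The trial asks sites for the tests that define a live secondary endpoint and then, on the wording of its change table, stops the results at the site. Every component of the endpoint is a laboratory or FISH result obtained at progression. Knowing only that a subject progressed does not give ISS stage, r-ISS stage or cytogenetic status, and no later analysis step can recover data that were not collected.

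The loss falls on late progressors. Treatment is capped at 36 months, so in Arm B these are largely subjects who progress after daratumumab has ended. They are central to the secondary objective of describing symptomatic myeloma that follows progression after daratumumab. Because Arm B is expected to progress more slowly, a larger share of its progressions falls after the switch, so the arms would not be ascertained equally.

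**Working it through.** **1. Is there another route for the results?**

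| Place | What it says | Does it restore the results? |
|---|---|---|
| Protocol 9.2.2 | Local determination of progression goes in the eCRF | No; the fact of progression only |
| Protocol 9.7 | Local laboratory data are entered in the eCRF for safety evaluation | No; the listed panel has no β2-microglobulin, LDH or FISH |
| Protocol 10.2 | A disease progression form is completed | Not stated; its content is not given |
| Protocol 9.2.5, 9.2.6, Table 10 | Tests at progression are done locally | Silent on reporting |

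**2. The plan's own figure.** Inputs from Protocol 11.2: HR 0.625, one-sided alpha 0.025, power 85%, 165 events. By Schoenfeld, events = 4(1.960 + 1.036)² / (ln 0.625)² = 162.6, so 163; 165 events give 85.5% power. The planning figure reproduces.

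**3. How many events fall after the switch?** Inputs:
- Medians 30 and 48 months, 180 per arm and 24-month accrual (Protocol 11.2); end at month 96 (Protocol 3.1).
- Assumed: exponential PFS, uniform accrual, no dropout.
- Switch month: the first-randomization date is not given. The original protocol is dated 19 July 2017, so Amendment 6 came at most about 86 months after first randomization. I use 72 to 86; the 72 is an assumption.

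With λ = ln 2 / median (0.02310 in A, 0.01444 in B), expected PFS events by month t are

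D(t) = 180 × [1 − (e^(−λ(t−24)) − e^(−λt)) / (24λ)].

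For Arm A at month 72: 180 × [1 − (0.3299 − 0.1895)/0.5545] = 134.4. For Arm B: 180 × [1 − (0.5000 − 0.3536)/0.3466] = 103.9.

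| Month | D, Arm A | D, Arm B | Later events to month 96, A / B | Share of arm's events to month 96, A / B |
|---|---|---|---|---|
| 72 | 134.4 | 103.9 | 19.4 / 22.3 | 12.6% / 17.7% |
| 86 | 147.0 | 117.9 | 6.8 / 8.4 | 4.4% / 6.6% |
| 96 | 153.8 | 126.2 | – | – |

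These are PFS events, so they include some deaths without progression and slightly overstate progressions. With 10% dropout per year, the counts after month 72 fall to 10.6 and 12.0.

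**4. Sensitivity to the treatment effect.** With a switch at month 82 and HR from 0.8 to 0.3, later events are 10.0 in A and 10.3 to 12.1 in B. The shares are 6.5% in A and 8.0% to 12.9% in B. The difference in counts is small; the larger Arm B share persists.

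**5. Effect on the endpoint in the unfavourable case.** Suppose missing results were scored as no adverse feature, all randomized subjects were the denominator, and the true adverse fraction q among events were equal in both arms. The B/A ratio of incidences is then D_B/D_A:
- complete data to month 96: 126.2/153.8 = 0.82
- loss from month 72: 103.9/134.4 = 0.77
- loss from month 86: 117.9/147.0 = 0.80

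The arm difference shifts by (22.3 − 19.4)/180 = 1.6 percentage points times q, or (8.4 − 6.8)/180 = 0.9 points times q. The documents do not give q. At an assumed 30% to 50% the shift is about 0.3 to 0.8 points, in favour of daratumumab.

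**The case against.** The non-reporting rule stands only in the summary of changes. The body keeps the tests, keeps a progression form and nowhere says that these results are withheld. This stands as a limit on the point: the body is silent on capture. It does not remove it, because the change table states the current amendment's own rule and nothing in the body makes an exception.

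Four stronger readings are tempting and the documents do not support them.

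- **Late progressors can never count.** The results remain in site records and could still be collected. Subjects who progressed by the primary analysis are unaffected.
- **They will be counted as having no adverse feature.** SAP 5.3.7.2 does not say so, and SAP 5.1.2 plans no imputation of missing efficacy values. If the denominator were progressors with results, the bias in step 5 would not arise in that form, although late progressors would still be unrepresented.
- **More subjects are lost in Arm B.** This is a planning projection worth about 2 to 3 events. The larger share of Arm B's events is the firmer statement.
- **The marrow at progression is done for nothing.** Clonal plasma cells are part of the Table 9 progression criteria and Table 10 requires morphology. The part unused by the trial is chiefly FISH.

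Two further points stand. Albumin is not needed for ISS III as SAP Table 3 defines it (β2-microglobulin of at least 5.5 mg/L alone), though Protocol 2.1.2 names it. And a SAP from 2020 cannot be faulted for not foreseeing a 2024 change in collection.

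**Conclusion.** The point holds as a gap in data capture. As written, Amendment 6 leaves the adverse-prognostic-features endpoint underivable from reported data for subjects who progress after it, and neither document closes the endpoint or says how such subjects are shown.

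The size is modest: about 7–19 PFS events in Arm A and 8–22 in Arm B, or 4–13% and 7–18% of each arm's events to month 96. This rests on the planning medians, no dropout and an assumed switch between months 72 and 86. Even with missing results scored as negative, the B/A ratio would move only from 0.82 to between 0.77 and 0.80, so a demonstrated bias should not be inferred.

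The endpoint has an interval and no test, and it lies outside the hierarchy of ORR, PFS2 and OS. Type I error and the primary result are unaffected. The correction is worthwhile because it is cheap and serves a stated secondary objective.

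**What to change.** Preferred: state in Protocol 9.2.5 and 9.2.6, and on the eCRF progression form, that β2-microglobulin, albumin, LDH and the four FISH probe results (del(17p13), amp(1q21), t(4;14), t(14;16)) at progression are reported to the sponsor as an exception to the non-reporting rule. In SAP 5.3.7.2, name the denominator and show progressors without these components as unknown, not as negative.

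Alternative: state in SAP 5.3.7 that this endpoint is closed at the primary-analysis cutoff and will not be updated in the addendum.

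The first route costs a few eCRF fields and minor site data entry for roughly 15 to 40 remaining progressions (6.8 + 8.4 to 19.4 + 22.3 events in the projection, deaths included), for tests already required. It is best done before older results become harder to retrieve. The second costs one sentence but gives up information on late progressors.

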1. INTRODUCTION

Daratumumab is a human immunoglobulin G1 kappa (IgG1κ) monoclonal antibody (mAb) that binds CD38 expressing malignant cells with high affinity. In the United States, intravenously (IV) administered daratumumab is indicated for use as follows: (1) in combination with lenalidomide and dexamethasone, or bortezomib and dexamethasone, for the treatment of patients with multiple myeloma who have received at least one prior therapy; (2) in combination with pomalidomide and dexamethasone for the treatment of patients with multiple myeloma who have received at least two prior therapies including lenalidomide and a proteasome inhibitor (PI); (3) as monotherapy, for the treatment of patients with multiple myeloma who have received at least 3 prior lines of therapy including a PI and an immunomodulatory agent (IMiD), or whose disease is refractory to both a PI and an IMiD. In the European Union, IV administered daratumumab is indicated for use as follows: (1) as monotherapy for the treatment of adult patients with relapsed and refractory multiple myeloma, whose prior therapy included a PI and an IMiD and who have demonstrated disease progression on the last therapy; (2) in combination with lenalidomide and dexamethasone, or bortezomib and dexamethasone, for the treatment of adult patients with multiple myeloma who have received at least one prior therapy. For other countries/territories, refer to the daratumumab label for the approved indication in that country.

For the most comprehensive nonclinical and clinical information regarding daratumumab, refer to the latest version of the Investigator's Brochure daratumumab. The term "sponsor" used throughout this document refers to the entities listed in the Contact Information page(s), which will be provided as a separate document.

1.1. Background

Disease Background

Multiple myeloma (MM) is thought to evolve from premalignant, asymptomatic plasma cell disorders such as (non-immunoglobulin [Ig]M) monoclonal gammopathy of undetermined significance (MGUS) or smoldering multiple myeloma (SMM), which are characterized by monoclonal plasma cell proliferation in the bone marrow without end-organ damage (Kyle 2009¹⁶, Kyle 2010¹⁵, Landgren 2009¹⁷, Weiss 2009³⁶). Smoldering multiple myeloma accounts for approximately 15% of all myeloma patients (Rios-Tamayo 2014³³). Several models for high-risk SMM have been proposed (Mateos 2016²⁴, Rajkumar 2013³⁰). According to these risk models, subjects with high-risk SMM have an approximate 50% risk of progression to MM within the first 2 years. This is in contrast to the lower risk of progression in the broader SMM population where it is estimated that 50% of patients will progress to MM within the first 5 years, equivalent to 10% per year (Rajkumar 2015³²). These models were developed prior to the update of the International Myeloma Working Group (IMWG) criteria for the diagnosis of SMM, ie, they included a population of ultra-high risk SMM patients, who are now considered to have MM. It is estimated that approximately 40% of all patients with SMM are at high-risk of progression to MM (Mateos 2013²³). Overall, approximately 50% of all patients with SMM are at high-risk of progression to MM, and 10% to 15% of those have been reclassified as MM under the 2014 SLiM criteria (Rajkumar 2015³²).

There is no approved treatment for patients with SMM. Outside of clinical studies, clinical management involves monitoring patients for the development of symptomatic disease (Landgren 2013¹⁸). Some early studies that investigated treatment for SMM with various chemotherapy regimens (melphalan-prednisone, thalidomide) or bisphosphonates did not show consistent clinical benefit (Dispenzieri 2013⁶, Landgren 2013¹⁸). A recent study (QuiRedex) of patients with high-risk SMM compared treatment with lenalidomide and dexamethasone (Rd, n=57) with observation (n=62). Rd treatment was associated with a significant delay in the progression to symptomatic MM (Mateos 2016²⁴). Median time to progression was not reached with Rd compared with 23 months for observation (hazard ratio [HR] 0.24, p<0.0001). Rd significantly improved overall survival (OS) (median not reached vs 117.6 months; HR 0.43, p=0.027) (Mateos 2016²⁴). In summary, these data have provided proof of concept that treatment of patients with SMM may prolong progression-free survival (PFS) and OS.

However, critiques have been put forward. In the QuiRedex study, mandatory evaluation for bone lesions was not required at baseline. The majority of progression events were related to bone disease, which raises the question of whether a portion of the subjects met criteria of symptomatic MM at the time of enrollment. Furthermore, the QuiRedex study was conducted prior to the 2014 update of the IMWG criteria for the diagnosis of MM. The new SLiM criteria include a bone marrow plasma cell content >60% or a serum (involved:uninvolved) free light chain (FLC) ratio >100 as well as >1 focal lesion on magnetic resonance imaging (MRI) imaging. This raises concern about whether data from the QuiRedex study are applicable to a population of patients who meet the current definition of SMM (Rajkumar 2014).²⁹ Rd is not without toxicities, and is not currently approved for the treatment of patients with SMM. In summary, a number of limitations of the QuiRedex study leave room to establish a less toxic treatment regimen for this asymptomatic patient population.

Nonclinical Studies

Pharmacology

Daratumumab is a human IgG1κ mAb that binds with high affinity to a unique epitope on CD38, a transmembrane glycoprotein. It is a targeted immunotherapy that attacks tumor cells that overexpress CD38, a transmembrane glycoprotein, in a variety of hematological malignancies including MM. Daratumumab induces lysis of CD38-expressing tumor cells, including MM tumor cells that were freshly isolated from patients, by a wide spectrum of mechanisms including complement-dependent cytotoxicity (CDC), antibody-dependent cell-mediated cytotoxicity (ADCC), antibody-dependent cellular phagocytosis, through activation of complement proteins, natural killer (NK) cells, and macrophages, respectively (de Weers 2011⁵, Overdijk 2015²⁸).

Clinical Studies

Daratumumab IV Monotherapy

Efficacy/Safety Studies

Daratumumab monotherapy induces deep and durable responses in subjects with heavily pretreated MM. Phase 2 Study 54767414MMY2002 (hereafter referred to as MMY2002) and Phase 1/2 Study GEN501 Part 2 (Part 1 was the dose-escalation phase of this first-in-human study) are ongoing single-arm, open-label studies in which subjects with relapsed and refractory MM are administered daratumumab IV as monotherapy weekly for 8 weeks, every 2 weeks for an additional 16 weeks, and every 4 weeks thereafter until disease progression or unacceptable toxicity. One hundred forty-eight (148) subjects treated with daratumumab 16 mg/kg administered IV were included in a combined analysis of efficacy in Study GEN501 and Study MMY2002. The overall response rate (ORR) for the combined data set was 31.1% (95% confidence interval [CI], 23.7%-39.2%). Responses included 3 subjects with stringent complete response (sCR; 2.0%), 4 subjects with complete response (CR; 2.7%), 13 subjects with very good partial response (VGPR; 8.8%), and 26 subjects with partial response (PR; 17.6%). Within the individual studies, the ORR was 35.7% (95%CI, 21.6%-52.0%) in Study GEN501 and 29.2% (95% CI, 20.8%-38.9%) in Study MMY2002. After a median duration of follow-up of 20.7 months, the Kaplan-Meier based median OS was 20.1 months (Usmani 2016³⁴).

Among 156 subjects treated with daratumumab 16 mg/kg IV in Studies GEN501, MMY2002, and 54767414MMY1002 (hereafter referred to as MMY1002) (a single-arm, open-label Phase 1 study of pharmacokinetics (PK) and safety conducted in Japanese subjects), 6 subjects (4%) discontinued daratumumab treatment due to a treatment-emergent adverse event (TEAEs). Three subjects (2%) died due to TEAEs. The most frequently reported TEAEs were fatigue (40%), nausea and anemia (28% each), back pain (26%), cough (24%), neutropenia (23%), pyrexia (22%), upper respiratory tract infection (22%), and thrombocytopenia (21%). Serious adverse events were reported in 33% of subjects; the most frequently reported serious adverse events were pneumonia (6%), pyrexia, hypercalcemia, and general physical health deterioration (3% each).

In the ongoing Phase 2 study 54767414SMM2001 (hereafter referred to as SMM2001), which evaluates daratumumab in SMM, single-agent activity in this population has been established in interim analysis 1 (March 2017). The safety profile of daratumumab in SMM2001 was consistent with what was observed in Studies GEN501, MMY2002, and MMY1002. For additional details regarding Study SMM2001, see Section 3.2.

Human Pharmacokinetics and Immunogenicity

Over the dose range from 1 to 24 mg/kg as daratumumab monotherapy or in combination with other treatments, increases in area-under-the-concentration-time curve were more than dose-proportional. Clearance decreased with increasing dose and repeated dosing, indicating target-mediated clearance. The mean (SD) estimated terminal half-life associated with linear clearance was approximately 18 (± 9) days.

Of the 199 subjects in Studies GEN501 and MMY2002 who were evaluable for immunogenicity, none were positive for anti-daratumumab antibodies; 2 (0.7%) of the 298 daratumumab combination therapy subjects analyzed were positive for anti-daratumumab antibodies.

For further details and the most up-to-date information about single-agent studies, please refer to the Investigator's Brochure (IB Daratumumab 2017 ¹¹).

Daratumumab SC Monotherapy

Study 54767414MMY1004 (hereafter referred to as MMY1004) is an ongoing, open-label, dose-escalation, Phase 1b study to assess the safety and PK of subcutaneous (SC) delivery of daratumumab. In Part 1 of this study, a mix and-deliver SC presentation (Dara-MD) of the currently approved daratumumab IV formulation was used: recombinant human hyaluronidase (rHuPH20) and daratumumab were mixed just prior to delivery. Up to 90 mL of Dara-MD was administered SC weekly for 8 weeks, every 2 weeks for 16 weeks, and then every 4 weeks thereafter. Preliminary data from this study show that SC administration results in acceptable PK, is efficacious, and has a substantially shortened administration time compared with standard IV administration. Part 2 of this study uses a new co-formulated preparation of daratumumab for SC administration (Dara-CF). Hereafter, Dara-CF will be referred to as Dara-SC. Updated information regarding daratumumab SC can be found in the Investigator's Brochure (IB Daratumumab 2017 ¹¹).

Efficacy

Fifty-three subjects (8 subjects in the 1200 mg cohort and 45 subjects in the 1800 mg cohort) were evaluable for efficacy. In the Dara-MD 1200-mg cohort, the ORR was 25% (95% CI: 3%-65%), both PRs; 1 was achieved at 8 weeks and the other at 20 weeks. In the Dara-MD 1800-mg cohort, 17 responses were observed for an ORR of 38% (95% CI: 24%-54%). One subject (2%) had a sCR, 3 subjects (7%) had VGPR, and 13 subjects (29%) had PRs. The median time to first response was 4 weeks (range, 4 to 8 weeks). In relapse or refractory MM, the antitumor activity of daratumumab 1800 mg SC (ORR 38%) was consistent with daratumumab 16 mg/kg IV (Usmani 2016³⁴).

Pharmacokinetics

CC1 -time curves following administration indicate a later time to maximum serum concentration (T_{max}) of approximately 72 hours post-dose, compared with IV administration when T_{max} occurs at or near the end of infusion. The 1800-mg SC dose achieved similar or higher maximum trough concentrations (C_{trough}) (the predose concentration on Cycle 3 Day 1) as 16 mg/kg IV and had similar variability. Preliminary analyses indicate that the bioavailability of Dara-MD is approximately 77% when administered SC.

Safety

Treatment-emergent adverse events for daratumumab administered SC appeared to be similar to those reported in single-agent studies of daratumumab administered IV, but with a lower incidence of infusion/injection-related reactions (IRRs) (Lokhorst 2015²⁰, Lonial 2016²¹). The incidence of all-grade IRRs was 13% and 24% in the Dara-MD 1200 mg and 1800 mg cohorts, respectively. By comparison, among subjects treated in single-agent or combination studies with IV daratumumab, IRRs were reported in 47% of subjects.

Administration of daratumumab in the abdominal SC tissue was associated with injection site erythema in 34% of subjects (1200 mg: 63%; 1800 mg: 29%) and induration 26% of subjects (1200 mg: 50%; 1800 mg: 22%).

